### **C. Rationale/Potential Benefits/Overview of Proposed Research**

**Intervention to increase positive emotions and promote health behaviors in cardiac patients.** There is clear evidence linking positive emotions with superior cardiac outcomes. Despite this, there has been minimal study of interventions in cardiac patients that specifically focus on the cultivation of positive emotional states. Though some programs have utilized relaxation or mindfulness, PP interventions had never been used in patients with HF until our pre-pilot study, despite their well-documented overall efficacy. Indeed, aside from our team's work to develop a PP-based intervention for post-ACS patients, we are aware of only one other trial that used PP in any cardiac population (outpatients with hypertension or undergoing angioplasty).

To address this gap in knowledge, we have created and optimized a novel PP-based health behavior intervention for patients with HF. A treatment cultivating positive emotions in this vulnerable population could provide broad and significant health benefits, and may have distinct—and more powerful—effects than simply attempting to dampen negative emotions. In the first phase of treatment development (IRB # 2015P000069), we performed qualitative research (N=32) to: (a) assess barriers to health behavior completion, (b) identify the causes and extent of positive emotional deficits, (c) examine potential links between positive emotional deficits and impaired health behaviors, and (d) inquire about the utility of potential PP and goal-setting exercises in participants with NYHA class II or III HF. Using this information we developed a customized, PP-based health behavior intervention based on these results and the existing literature, which we tested during phase two of this project (IRB # 2016P001443). Though follow-up is ongoing, preliminary analyses after 5 participants revealed that the intervention was feasible, subjectively helpful, and associated with significant immediate improvements in happiness and numerical improvements in positive affect and moderate to vigorous physical activity. Using feedback from participants and the data from this proof-of-concept trial, we have created an optimized version of the intervention. We now wish to test the feasibility and efficacy of the optimized intervention in a three-arm, randomized pilot trial.

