**(a) Physical activity (primary health behavior outcome measure).** We selected physical activity as our main health behavior outcome for several reasons. Physical activity is a key modifiable prognostic factor in HF patients and has been associated with improved exercise capacity, QoL, and survival in this population. Furthermore, there are established links between higher levels of positive emotions (particularly optimism) and increased physical activity, suggesting that a PP intervention could impact this behavior. Finally, increasing physical activity is likely to require a relatively broad approach, as compared to other behaviors, which may improve with simple interventions such as electronic reminders.

Physical activity will be measured using the ActiGraph GT3X+ three-axis accelerometer (ActiGraph, LLC, Pensacola, FL). Accelerometers are often considered to be the standard for measuring habitual physical activity. ActiGraph GT3X+ step counters are validated as measures of physical activity and have been used in numerous studies of physical activity in patients with medical illness. We chose to use ActiGraph GT3X+ accelerometers because they are the most widely used monitors for research purposes and adequately discriminate between different levels of activity. In this trial, participants will wear the accelerometer (for 1 week at baseline and 1 week at each follow-up time point) to assess the feasibility of doing so, ensure adequate capture of physical activity, and examine the impact of the intervention on this health behavior. We will measure the number of steps taken daily and the amount of time spent in moderate to vigorous physical activity (MVPA) to examine the impact of the intervention on these important outcomes. We will turn off all notifications on the device prior to the start of the study. We will require at least 480 minutes of wear time to be considered a valid day, and at least 5 valid days for a participant's data to be considered complete. If a participant does not provide at least this much data, we will ask the participant to re-wear the step counter until information from at least 5 valid days has been captured.

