**(a) Optimism** will be measured using the Life Orientation Test-Revised (LOT-R), a well-validated 6-item instrument, and the State Optimism Measure (SOM). Dispositional optimism is the positive psychological state most linked to cardiac outcomes, and the LOT-R has been used to measure optimism in many studies of cardiac patients. Though dispositional optimism theoretically would be stable over time, research suggests that LOT-R scores can change quickly in response to psychological interventions. We also will be using a short scale developed by our team (SOM) to measure state optimism.

**(b) Positive affect** (primary psychological outcome measure) will be measured using the positive affect items on the Positive and Negative Affect Schedule (PANAS), a well-validated scale used in other intervention trials and in patients with HF.

**(c) Anxiety and depression** will be measured using the anxiety and depression subscales of the Hospital Anxiety and Depression Scale (HADS). This well-validated scale has been used in many studies of patients with heart disease (including our group’s studies), and has the advantage of having few somatic symptom items that can confound mood/anxiety assessment in medically-ill patients.

**Measurement of physical outcomes.** We will also assess selected physical outcomes.

**(a) Cardiac symptoms and HF-related QoL** (primary functional outcome measure) will be measured with the Kansas City Cardiomyopathy Questionnaire (KCCQ), a well-validated questionnaire of health status in HF. The full scale will be used to measure HF-specific health-related QoL (HRQoL), and an eight-question subset of the KCCQ will be used as a measure of HF symptoms. The KCCQ is a valid, reliable, and responsive instrument in patients with HF and is strongly correlated with NYHA class. We chose the KCCQ as our primary functional

outcome measure because it likely would be affected by all three of our health behaviors of interest (physical activity, medication adherence, and diet).

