#### Measures:

- Optimism: LOT-R; SOM
- Positive affect: PANAS (primary outcome measure for this aim)
- Anxiety/depression: HADS

We will examine between-group differences (PP-based condition vs. MI-informed educational control and PP-based condition vs. TAU) on changes in each of these psychological outcomes to assess the impact of the intervention compared to both an active control and TAU. The primary study endpoint will be 12 weeks, though we will secondarily assess the impact of the intervention on outcomes at 24 weeks as well.

**Aim #3 (Impact on functional outcomes and health behaviors):** To examine the impact of the intervention on physical activity (steps, as measured by accelerometer; primary health behavior outcome), medication adherence, sodium intake, HF-related QoL, and generic HRQoL, compared to treatment as usual and an MI-based health behavior education intervention.

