**C. Statistical methods**

Data will be downloaded from REDCap into the Stata statistical package. For Aim 1 (feasibility, acceptability), descriptive statistics will be used to report proportion of exercise completion and mean scores on exercise ratings of ease and utility. To examine the immediate impact of the intervention on positive affect and optimism, we will use linear mixed models (to account for within-person correlations) to examine the improvement in these scores from pre- to post-exercise.

For our secondary aims, we will initially compare physical activity (# of steps/day) at 12 and 24 weeks between groups using a Wilcoxon rank sum test, given that the distribution of the number of steps will likely be skewed. In addition, we will compare between-group differences in change over time in all self-report measures (including psychological, functional, and health behavior outcomes) at the 12 and 24-week time points using random effects regression models with a random intercept for each patient. All statistical tests will be two-tailed, with  $p < .05$  considered significant.

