**D. Power analysis**

We have performed power analyses assuming 20 participants in each group. To account for potential drop outs between enrollment and randomization, we will enroll 75 participants with a goal of randomizing 60. This pilot trial is not designed to detect significant between-group differences in 12- or 24-week health behavior outcomes, but is powered to meet our primary aims of feasibility and immediate impact. For feasibility, 75-80% of subjects have completed the majority of PP exercises in our prior work, and 90% completed the majority of PP exercises in our proof-of-concept trial in patients with HF. With 20 PP participants, we will have at least 80% power to detect a difference between our expected proportion of participants completing at least 5 out of 8 PP exercises (80%) and the null hypothesis (true proportion of 50% or less) at the

two sided 0.05 level using a binomial proportion test. In a prior study, we found that PP interventions led to a moderate ( $d=.52$ ) improvement in optimism immediately post-exercise. If we assume completion of ~140 exercises from 20 subjects and a within-person correlation of 0.5 for change in pre-/post- ratings across exercises, our proposed study is powered at over 80% to detect a similar effect size improvement of optimism immediately post-exercise at the two-sided 0.05 level.

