#### **B. Potential Benefits to Society**

Increasing positive psychological states in cardiac patients may have important public health benefits. Optimism and other positive affective states are prospectively associated with increased participation in healthy behaviors and with superior cardiac outcomes. The creation of

a PP-based intervention—based on the previous qualitative research phase—targeted at improving positive emotional states in HF patients could lead to a novel approach to enhancing adherence in this population, which in turn might result in decreased morbidity and mortality in this population. Future studies could investigate the feasibility of implementing this intervention in a similar population and examine the impact on cardiac and psychological outcomes. If the PP-based health behavior intervention in this study proves to be feasible, well-accepted, and associated with improvements in physical activity and other key outcomes, it may well be possible to utilize these easily-delivered and completed exercises as part of a clinical care package for HF patients. Thus participation in this study may result in substantial benefit to future patients.

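### Section VI.C declares any between-group p < .05 significant, although three domain-level primary measures are each tested against two unranked controls; these comparisons should be labelled exploratory

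*Combined protocol and SAP*

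**What the plan says.** Section VI.C describes a rank-sum comparison of steps per day and random-effects models for all self-report scales, at 12 and 24 weeks. One rule then covers everything: "All statistical tests will be two-tailed, with $p < .05$ considered significant".

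Under both Aim 2 and Aim 3, section VI.A and B names the same pair of contrasts, "PP-based condition vs. MI-informed educational control and PP-based condition vs. TAU", and puts neither first.

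Three outcomes in these aims are labelled primary for their domain:
- PANAS positive affect is the lead psychological measure (V.E, and VI.A and B under Aim 2).
- Steps per day is the lead health behavior measure. V.E has "Physical activity (primary health behavior outcome measure", and Aim 3 repeats the label.
- KCCQ is the "primary functional outcome measure" in V.E. That label does not recur in section VI.

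The plan does contain some ordering. Feasibility is the trial's primary outcome (II; VI.A and B). VI.C introduces the between-group comparisons as belonging to the secondary aims. VI.A and B, in the Aim 2 text, puts week 12 ahead of week 24. VI.D adds: "This pilot trial is not designed to detect significant between-group differences in 12- or 24-week health behavior outcomes".

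Statements of intent differ. The numbered list in I.C speaks of exploring possible benefits. The hypotheses for Aims 2 and 3 in section II predict significance only for pre-post change, and merely numerically larger gains against the controls. Yet I.C also says "We now wish to test the feasibility and efficacy of the optimized intervention in a three-arm, randomized pilot trial". The section on benefits to society considers use in clinical care if the programme is feasible, well accepted and "associated with improvements in physical activity and other key outcomes".

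**The concern.** Followed literally, VI.C lets any one of six week-12 comparisons on domain-leading measures be reported as a significant between-group effect. Nothing in section VI says which measure or which control would carry such a statement. The caveat in VI.D does not fully close the gap: it names health behavior outcomes only, so on its wording it covers steps but not PANAS or KCCQ, and the VI.C rule would still call a nominal result on steps significant.

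The two contrasts also answer different questions. PP versus TAU includes the effect of weekly contact and education; PP versus MI holds much of that constant. Sections V.A and VI.A and B recognise the difference in purpose, but VI.C has no rule for which contrast supports a statement about the PP content.

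What is at stake is how secondary results are described. The primary feasibility conclusion does not depend on it.

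**Working it through.** **The plan's own figures (VI.D).**
- Feasibility: n = 20, 80% against 50%, two-sided 0.05. Rejecting at 15 or more of 20 gives alpha 2 × 0.0207 = 0.041 and power P(X ≥ 15 | 0.8) = 80.4%. This agrees with the stated 80% or more.
- Immediate impact: 140/20 = 7 exercises per person; design effect 1 + 6 × 0.5 = 4; effective n = 140/4 = 35. Power is Φ(0.52 × √35 − 1.96) = Φ(1.12) = 86.8%, or 83.1% using t with 19 df. This agrees with the stated figure of over 80%.
- The plan gives no family-wise error rate for Aims 2 and 3, so there is nothing to reproduce there.

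**Inputs for the check.** Three labelled measures (V.E; VI.A and B), two contrasts each (VI.A and B), week 12 only, 20 per arm (VI.D), two-sided 0.05 per test (VI.C). The week-12 sentence stands under Aim 2; I take it to cover Aim 3 too. The other scales and week 24 are left out because the plan places them lower. The correlation r between outcomes is not given, so it is varied from 0 to 0.8.

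**Number of tests.** 3 × 2 = 6.

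**If all six were independent.** 1 − 0.95^6 = 26.5%.

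**Shared PP arm.** With equal arms, the correlation between the two contrasts is (σ²/20)/(2σ²/20) = 0.5. The chance of at least one p < .05 for one measure is then 9.07%. For three uncorrelated measures it is 1 − (1 − 0.0907)^3 = 24.8%.

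**Correlated measures.** Simulation of the six z statistics (one million draws per row, correlation r across measures and 0.5 across contrasts), with no true effect:

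| r | At least one p < .05, either direction | At least one favouring PP | PP better than both controls on the same measure |
|---|---|---|---|
| 0 | 24.8% | 13.0% | 1.4% |
| 0.3 | 23.8% | 12.0% | 1.4% |
| 0.5 | 21.9% | 11.0% | 1.3% |
| 0.7 | 19.1% | 9.6% | 1.1% |
| 0.8 | 17.3% | 8.7% | 1.0% |

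**Against a single test.** In either direction: 17.3/5 = 3.5 to 24.8/5 = 5.0 times the nominal rate. Favouring PP: 8.7/2.5 = 3.5 to 13.0/2.5 = 5.2 times.

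**Check with 20 per arm.** t tests on simulated change scores gave 24.9%, 24.3%, 22.0% and 17.4% at r = 0, 0.2, 0.5 and 0.8. A version nearer to VI.C (rank-sum for steps, statistics for the other two measures referred to 1.96) gave 27.0%, 25.8% and 23.9% at r = 0, 0.3 and 0.5, with 14.3%, 13.4% and 12.2% favouring PP. It runs slightly higher because 1.96 is a little liberal at this sample size.

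**The case against.** The strongest reply is that the plan already treats these comparisons as subordinate. They are secondary aims, feasibility is primary, week 12 outranks week 24, and each primary label leads its own domain, so pooling the three into one family is the reviewer's choice. The success criteria in VI.A and B cover session completion, accelerometer data, acceptability and immediate impact; none is a between-group p-value. All of this stands, and it is why the point is minor. It does not say which of the six tests counts, and secondary is not the same as exploratory while VI.C still declares significance.

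Several stronger readings are tempting, and the documents do not support them:
- *That the plan has no hierarchy.* It has the tiers just listed. What is missing is a ranking among the three measures and between the two controls.
- *That a useless programme would be declared beneficial in about a fifth of trials.* A single figure of 22% requires an assumed r near 0.5 and counts results in which PP looks worse. The chance of a false benefit is about 9-13%.
- *That progression to a larger trial turns on p < .05.* No section says so. The review after 12 participants (VIII.C) rests on acceptability, optimism ratings, dissatisfaction and session completion. The efficacy wording in I.C and the benefits paragraph are not decision rules.
- *That a PP versus TAU difference due to attention would be an error.* V.A says the TAU arm serves to show overall impact and describes MI as the attention control. If PP truly beats TAU through contact alone, a significant PP versus TAU result answers that question correctly. Only attributing it to the PP content would be wrong.
- *That a formal adjustment is required.* Bonferroni at 0.05/6 = 0.0083, also the first Holm step, would hold the rate below 5%. But 80% power at that level needs a difference of about 1.15 SD with 20 per arm, a debatable trade in a pilot.

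**Conclusion.** The concern holds in a limited form. VI.C attaches the word significant to six week-12 comparisons on domain-leading measures without a multiplicity statement, a ranking of measures or controls, or an exploratory label in section VI. With no true effect, at least one of the six reaches p < .05 in about 17-25% of trials, and about 9-13% show at least one such result favouring PP. These figures assume 20 analysed per arm, approximately normal test statistics and an outcome correlation between 0.8 and 0. The check closer to the planned tests runs a few points higher for correlations of 0 to 0.5.

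The rule also exceeds the plan's own intent in I.C and II, which is to explore benefits and look for numerically larger gains against the controls. The consequence is confined to how secondary findings are reported, so the point is minor.

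**What to change.** In VI.C:
1. Keep the two-sided p < .05 criterion for the Aim 1 tests (the feasibility binomial test in VI.D and the immediate-impact models) and for the pre-post hypotheses of Aims 2 and 3 in section II. Restricting it to immediate impact alone would leave those without a criterion.
2. State that all between-group comparisons under Aims 2 and 3 are exploratory, and are reported as differences with 95% confidence intervals and no declaration of significance. This also extends the spirit of the VI.D caveat to PANAS and KCCQ.
3. Carry the reasoning of V.A into VI.C: PP versus TAU estimates the overall effect including attention, and any statement about an effect specific to PP rests on PP versus MI.

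The cost is a few sentences, with no extra data or participants. The downside is that an isolated nominal p < .05 between groups can no longer be called significant. The change should be made before the between-group data are analysed.

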**D. Power analysis**

We have performed power analyses assuming 20 participants in each group. To account for potential drop outs between enrollment and randomization, we will enroll 75 participants with a goal of randomizing 60. This pilot trial is not designed to detect significant between-group differences in 12- or 24-week health behavior outcomes, but is powered to meet our primary aims of feasibility and immediate impact. For feasibility, 75-80% of subjects have completed the majority of PP exercises in our prior work, and 90% completed the majority of PP exercises in our proof-of-concept trial in patients with HF. With 20 PP participants, we will have at least 80% power to detect a difference between our expected proportion of participants completing at least 5 out of 8 PP exercises (80%) and the null hypothesis (true proportion of 50% or less) at the

two sided 0.05 level using a binomial proportion test. In a prior study, we found that PP interventions led to a moderate ( $d=.52$ ) improvement in optimism immediately post-exercise. If we assume completion of ~140 exercises from 20 subjects and a within-person correlation of 0.5 for change in pre-/post- ratings across exercises, our proposed study is powered at over 80% to detect a similar effect size improvement of optimism immediately post-exercise at the two-sided 0.05 level.

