## **II. SPECIFIC AIMS**

**Specific Aim #1 (Feasibility [primary outcome], acceptability, immediate impact):** To assess the feasibility, acceptability, and immediate impact of the PP-based health behavior intervention

on optimism and happiness in a three-arm (N=75), randomized, controlled pilot trial.

*Hypothesis: The PP intervention will be feasible (the majority of participants will complete at least 7 of 12 sessions/exercises) and acceptable (mean score of at least 6 out of 10 on ratings of ease of completion and subjective helpfulness of the exercises) and will have adequate immediate impact on positive affect and optimism (post-exercise ratings of positive affect and optimism will be higher than pre-exercise ratings (measured by pre- and post- measurements on a Likert scale).*

**Specific Aim #2 (overall impact on psychological health):** to examine the intervention's overall impact on both positive (positive affect, optimism) and negative (depression, anxiety) psychological health, compared to TAU and an MI-based educational control condition.

*Hypothesis: The intervention will lead to significant pre-post increases in positive affect and optimism and significant reductions in depression and anxiety. Compared to the control conditions, the PP-based intervention will lead to greater numerical improvements in all psychological outcomes.*

**Specific Aim #3 (adherence and functional outcomes):** To examine the impact of the intervention on physical activity (steps, as measured by accelerometer; primary health behavior outcome), medication adherence, sodium intake, HF-related QoL, and generic HRQoL, compared to TAU and an MI-based educational control condition.

*Hypothesis: The intervention will lead to significant pre-post improvements in adherence and functional outcomes at follow-up and will lead to greater numerical improvements in these outcomes compared to the treatment as usual and the MI-based control condition.*

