#### Measures:

- Rates of completion of exercises (recorded by study trainer).
- Successful use of ActiGraph accelerometer.
- Patient rating of immediate outcomes on 10-point Likert scale: Ease of completion, overall utility, change in positive affect and optimism from pre- to post-exercise.

The intervention will be considered feasible if  $\geq 7$  of the 12 sessions are completed by a majority of patients. The objective assessment measures will be considered feasible if we obtain adequate physical activity data (at least 5 valid days of accelerometer wear time) in at least 80% of enrolled participants at one of the follow-up time points. The PP exercises will be considered to be acceptable if participants have mean scores of at least 6/10 on the ratings of ease of completion and subjective helpfulness across exercises. The PP exercises will be considered to have adequate impact if participants rate positive affect and optimism significantly higher post-exercise than pre-exercises across exercises (via mixed linear models).

**Aim #2** (*overall impact on psychological health*): To examine the intervention's impact on both positive (positive affect, optimism) and negative (depression, anxiety) psychological health, compared to TAU and a MI-based educational control condition.

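### Over 80% power is shown for optimism alone, but the immediate-impact criterion needs both positive affect and optimism to rise significantly, and power for that is not shown

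*Combined protocol and SAP*

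**What the plan says.** Section II, Aim #1, hypothesizes that the intervention "will have adequate immediate impact on positive affect and optimism", and explains this as "post-exercise ratings of positive affect and optimism will be higher than pre-exercise ratings". Section VI.A and B, under the Aim #1 measures, turns this into a decision rule: the exercises have "adequate impact if participants rate positive affect and optimism significantly higher post-exercise than pre-exercises across exercises", judged by mixed linear models. Section VI.C likewise plans mixed models for both ratings.

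Section VI.D describes the pilot as not designed to find between-group differences in health behavior at 12 or 24 weeks, "but is powered to meet our primary aims of feasibility and immediate impact". The support for the second of those aims is a single calculation, which ends: "our proposed study is powered at over 80% to detect a similar effect size improvement of optimism immediately post-exercise". Its inputs are d = 0.52 from a prior study, about 140 completed exercises from 20 participants, a within-person correlation of 0.5 across exercises, and a two-sided 0.05 level. Nowhere do the documents give an effect size or power for positive affect, or a correlation between changes in the two ratings.

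**The concern.** The rule and the calculation do not describe the same event. The rule is met only if two tests are both significant; the calculation gives the chance that one of them is. Unless success on optimism practically guarantees success on positive affect, the chance of meeting the rule is lower than the figure given.

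Immediate impact is one of the two aims for which section VI.D claims power, and a pilot of this kind informs whether to go on. A reader would take the risk of failing the criterion, given an effect of the assumed size, to be under 20%. If the true risk is higher, a failed criterion could be read as evidence of no impact when it reflects a demanding rule applied to 20 people.

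**Working it through.** **Inputs from section VI.D:** 20 participants; about 140 exercises, so 140/20 = 7 each; within-person correlation 0.5; d = 0.52 for optimism; two-sided 0.05.

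**Assumptions, not in the documents:** the effect size for positive affect; the correlation ρ between participants' mean changes in the two ratings; the same within-person correlation (0.5) for positive affect; and the reference distribution, because section VI.C names linear mixed models without a degrees-of-freedom method. I show both a t test with 19 df (20 participants as the independent units) and the normal approximation.

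**Step 1. The plan's own figure, optimism alone.**
- Design effect = 1 + (7 − 1) × 0.5 = 4.
- Effective n = 140/4 = 35.
- Noncentrality = 0.52 × √35 = 3.076.
- Normal: Φ(3.076 − 1.960) = Φ(1.116) = 86.8%.
- Noncentral t, 19 df: 83.1%.

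The statement of over 80% reproduces by either method.

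**Step 2. What follows without further assumptions.** The probability that two tests are both significant is at most the smaller of the two separate probabilities. The optimism figure is therefore a ceiling for the criterion, not its power.

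**Step 3. Joint power, optimism d = 0.52 throughout.** The normal column uses the bivariate normal distribution. The t column uses simulation of two correlated one-sample t tests on 20 participant means.

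| Assumed d, positive affect | ρ | t, 19 df | Normal |
|---|---|---|---|
| 0.52 | 0 | 69% | 75% |
| 0.52 | 0.5 | 73% | 78% |
| 0.52 | 0.7 | 75% | 80% |
| 0.52 | 0.8 | 76% | 81% |
| 0.52 | 0.9 | 78% | 83% |
| 0.40 | 0 to 0.9 | 51–61% | 57–65% |
| 0.60 | 0.7 | 80% | 85% |
| 0.70 | 0 | 81% | 86% |

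The first row can be checked by hand, since at ρ = 0 joint power is the product: 0.831² = 0.69 and 0.868² = 0.75.

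**Step 4. Reading the table.** With equal effects, the t version stays below 80% for ρ up to 0.9, while the normal version passes 80% from about ρ = 0.7. A larger effect on positive affect lifts the t version above 80% at moderate or even zero correlation. A smaller one puts joint power well below 80% by either method.

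**The case against.** The strongest reply is that section VI.D contains no wrong number. The sentence giving the figure names optimism explicitly and makes no claim about two tests, and the figure is correct. That stands: the fault lies in the general sentence, which extends the result to the whole immediate-impact aim.

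Second, any joint figure needs inputs that the protocol does not supply. That also stands. The same person gives both ratings at the same moments on the same kind of scale, so a correlation of 0 is the least plausible value, and it is what produces the low end of each range. With a high correlation and the normal approximation, or with a larger effect on positive affect, the criterion does have more than 80% power.

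A reader might therefore infer either of two stronger things, and the documents support neither. One is that the trial is underpowered for its criterion by a known amount; the amount depends on an effect size and a correlation that are not stated. The other is that requiring two significant results raises the false-positive risk; a rule that needs both tests to succeed does not inflate type I error.

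Third, this is a pilot, and only feasibility carries the label of primary outcome in section II. That limits the weight of the point. It does not remove it, because section VI.D itself counts immediate impact among the primary aims and claims power for it.

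**Conclusion.** The claim of adequate power is shown for optimism and not for the two-part criterion that the trial will apply. With d = 0.52 assumed for both ratings and a correlation of 0 to 0.9, joint power is about 69% to 78% with t tests on 19 df, or 75% to 83% by the normal approximation. On the t version, an intervention with exactly the assumed effects would miss the criterion about 22% to 31% of the time. If positive affect has d = 0.40, joint power is about 51% to 65% across both methods; if d = 0.70, it is above 80%. In no case can it exceed the 83% (t) or 87% (normal) for optimism alone. This is a mismatch between a decision rule and its justification, worth correcting but not a threat to the trial's validity.

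**What to change.** In section VI.D, limit the statement of over 80% power, and the claim of being powered for immediate impact, to optimism. Then report power for the two-part criterion as a conditional range, stating the assumed effect size for positive affect, the assumed correlation between the two ratings, and the test used.

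Alternatively, before any data are seen, amend section VI.A and B so that optimism is the deciding rating and positive affect is supportive. The existing calculation would then match the rule.

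The first option costs wording only and makes the stated power somewhat less favorable. The second keeps the stated power but narrows what a success would show. Neither needs more participants or more data.
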